9.4. Data sources

Data for this study will be obtained from SNDS database, which covers >99% (~ 65 million insures) of the French population from birth or immigration to death or emigration. The SNDS includes longitudinal claims data for inpatient and outpatient encounters by combining 3 main databases: the national hospital discharge database (PMSI), the health insurance claims database (Système National d'Informations Inter-Régimes de l'Assurance Maladie, SNIIRAM) and the national death registry. The PMSI was established in 2006 and captures information relating to inpatient or ambulatory care admissions to a public or private hospital in France. The SNIIRAM database captures data on socioeconomic characteristics and medical claims for medications, procedures and laboratory tests since 2003. The SNIIRAM database also includes the LTD registration data which captures information on the presence of LTD for which patients are eligible for 100% reimbursement of healthcare for the given disease. Data in the SNDS are updated bi-annually. Only variables relevant to this study, and available in the SNDS database, will be extracted.

As per the General Data Protection Regulation policy, only aggregated data with sample sizes >5 patients will be used for communications.

Details on the Health Insurance Data system, SNDS, are provided below in Table 4.

Table 4. Summary of Système National des Données de Santé database

Characteristics	SNDS
Database type	Claims
Country population	Over 65 million
Overall representativeness	Approximately 99% of the French population
Physician population	All
Expected number of tofacitinib	About 5,300 ^a
patients by the end of 2019	
Lag in data availability	12 months ^b

a Based on tofacitinib data from 2017-2019 that were obtained using the publicly available tools for querying the French national health registers

9.5. Study size

Comparative analyses for the changes in the proportions of patients with risk factors

For the comparative analyses, the study will assess changes in the proportion of tofacitinib initiators with risk factors of interest (e.g., VTE, elderly, CV, and malignancy) over different reporting periods (Section 9.2.4-9.2.6). The primary comparison of interest will be the proportion of tofacitinib initiators with risk factors during reporting period 3 (when full implementation of the updated aRMMs is expected) against that during reporting period 1 (baseline before implementation or notification of updated aRMMs). Secondary comparisons

b Data are updated once a year, usually by the end of August

of interest will be between reporting period 1 and reporting period 2, as well as reporting period 2 and reporting period 3 to assess any intermediate changes.

Sample size required for evaluating changes in the proportion of patients with risk factors across reporting periods was calculated using the following formula based on two independent sample *z*-test for proportions:⁸

$$N= \frac{(z_{\alpha/2}+z_{\beta})^2(p_1(1-p_1)+p_2(1-p_2))}{\epsilon^2}$$

Preliminary data from the first interim report of the ongoing DUS study (A3921321) suggests that 30 to 80% of tofacitinib initiators had one or more risk factors of interest at baseline (e.g., during reporting period 1). Sample size was calculated across a range of possible baseline proportions and meaningful differences between any two reporting periods. Given the challenges in defining minimum meaningful differences and the lack of scientific guidance or validated thresholds, Chen et al.'s rule of thumb for classifying the magnitude of effect size based on odds ratios (OR) (e.g., small effect) is used to inform the minimum meaningful difference. Minimum sample size is determined based on the smallest sample size needed to detect a minimum meaningful difference per scenario of baseline proportion. It is thus estimated that 160 to 354 patients per reporting period (480 to 1,062 total patients) per indication group (e.g., RA/PsA and UC) are needed to detect a minimum meaningful difference with 80% statistical power ($\beta = 0.20$) and a two-sided 5% significance level ($\alpha = 0.05$) (Table 1**Error! Reference source not found.**). Sample size needed varies based on the baseline proportion and point percent difference between reporting periods. The required sample size is irrespective of the length of the reporting period.

Table 5.	Sample size for comparing changes in the proportion of patients with risk
	factors of interest across reporting periods

Percentage of patients with at least one risk factors at baseline	Point percent difference between any two reporting periods	Effect size classification for the difference based on OR ^a	Number of patients needed per reporting period ^b	Total number of patients needed for the entire study period per indication group b, c
80%	10%	Small	291	873
70%	10%	Small	354	1,062
70%	15%	Small	160	480
60%	10%	Small	385	1,155
60%	15%	Small	171	513
50%	10%	Small	385	1,155
50%	15%	Small	167	501
40%	10%	Small	354	1,062
30%	10%	Small	291	873

Odds ratio = VTE reporting period X odds of outcome / VTE reporting period Y odds of outcome; Classified effect sizes as weak ($1 \le OR < 1.5$), small ($1.5 \le OR < 2$), medium ($2 \le OR < 3$) and large (≥ 3).

Comparative analyses for the changes in composite risk factor scores

For the comparative analyses that assess changes in the composite risk factor scores (e.g., mean number of risk factors per patient where each risk factor receives a score of 1) across reporting periods, the sample size was calculated using the following formula based on two independent sample *t*-test⁸:

$$N= \frac{2(z_{\alpha/2}+z_{\beta})^2\sigma^2}{\epsilon^2}$$

Preliminary data from the first interim report of the ongoing DUS study (A3921321) suggests the standard deviation for the mean number of risk factors per patient had a wide range but frequently centred around 0.6 to 0.8 at baseline (e.g., reporting period 1). Sample size was calculated across a range of standard deviations and differences in the mean number of risk factors per patient assuming equal sample sizes and variances between any two reporting periods. Given the challenges in defining minimum meaningful differences and the lack of scientific guidance or validated thresholds for the composite risk factor scores, Cohen's *d* effect size of 0.2 to <0.5 (small effect) was used to inform the minimum meaningful difference. Minimum sample size is determined based on the smallest sample size needed to detect a minimum meaningful difference per scenario of baseline variance. It is estimated that 80 to 142 patients per reporting period (240 to 426 total patients) per indication group (e.g., RA/PsA and UC) are needed to detect a minimum meaningful difference with 80%

^a References:^{9, 10}

^b Assuming equal sample size across reporting period

^c Bolded rows indicate minimum sample size required per scenario of proportions

statistical power (β = 0.20) and a two-sided 5% significance level (α = 0.05) (Table 6). Sample size needed varies based on the baseline variance and difference in the mean number of risk factors between reporting periods. The required sample size is irrespective of the length of the reporting period.

Table 6. Sample size for comparing changes in the mean number of risk factors per patient across reporting periods

Standard deviation for the mean number of risk factors per patient	Difference in the mean number of risk factors between any two reporting periods	Cohen's d effect size ^a	Number of patients needed per reporting period ^b	Total number of patients needed for the entire study period per indication group b, c
1.3	-0.20	Small	664	1992
1.3	-0.25	Small	425	1275
1.3	-0.30	Small	295	885
1.3	-0.35	Small	217	651
1.3	-0.40	Small	166	498
1.3	-0.45	Small	132	396
1.3	-0.50	Small	107	321
1.3	-0.55	Small	88	264
1.2	-0.20	Small	566	1698
1.2	-0.25	Small	362	1086
1.2	-0.30	Small	252	756
1.2	-0.35	Small	185	555
1.2	-0.40	Small	142	426
1.2	-0.45	Small	112	336
1.2	-0.50	Small	91	273
1.1	-0.20	Small	475	1425
1.1	-0.25	Small	304	912
1.1	-0.30	Small	212	636
1.1	-0.35	Small	156	468
1.1	-0.40	Small	119	357
1.1	-0.45	Small	94	282
1.0	-0.15	Small	698	2094
1.0	-0.20	Small	393	1179
1.0	-0.25	Small	252	756
1.0	-0.30	Small	175	525
1.0	-0.35	Small	129	387
1.0	-0.40	Small	99	297

Table 6. Sample size for comparing changes in the mean number of risk factors per patient across reporting periods

Standard deviation for the mean number of risk factors per patient	Difference in the mean number of risk factors between any two reporting periods	Cohen's d effect size ^a	Number of patients needed per reporting period ^b	Total number of patients needed for the entire study period per indication group b, c
0.9	-0.15	Small	566	1698
0.9	-0.20	Small	318	954
0.9	-0.25	Small	204	612
0.9	-0.30	Small	142	426
0.9	-0.35	Small	104	312
0.9	-0.40	Small	80	240
0.8	-0.15	Small	447	1341
0.8	-0.20	Small	252	756
0.8	-0.25	Small	161	483
0.8	-0.30	Small	112	336
0.8	-0.35	Small	83	249
0.7	-0.15	Small	342	1026
0.7	-0.20	Small	193	579
0.7	-0.25	Small	124	372
0.7	-0.30	Small	86	258
0.6	-0.10	Small	566	1698
0.6	-0.15	Small	252	756
0.6	-0.20	Small	142	426
0.6	-0.25	Small	91	273
0.5	-0.10	Small	393	1179
0.5	-0.15	Small	175	525
0.5	-0.20	Small	99	297
0.4	-0.10	Small	252	756
0.4	-0.15	Small	112	336
0.3	-0.10	Small	142	426

- a. Reference:¹⁰
- b. Assuming equal sample size across reporting period
- c. Bolded rows indicate minimum sample size required per scenario of baseline variance

Through a preliminary assessment, the SNDS database holds records for approximately 4,000 RA or PsA patients and 1,000 UC patients who initiated tofacitinib between January 2018 (start of indexing period) and December 2020. It is projected that approximately 8,000

RA or PsA and 2,000 UC patients who initiate to facitinib will be captured through the end of the indexing period (e.g., December 2024).

Based on these estimated numbers of patients during the entire study period and sample size calculation, the study is anticipated to have sufficient sample size to detect meaningful differences in the use of tofacitinib among patients with risk factors between the pre- and post-implementation period of updated aRMMs. All eligible patients during the study period will be included in the analysis. The number of patients will be actively monitored during the course of the study and the MAH will provide timely notification to the EMA if sufficient sample size is not reached during the planned study period.

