Variables: Demographic characteristics (age and sex), diagnoses (indication [including off-label use]), comorbidities, contraindicated use, VTE risk factors, CV risk factors and malignancy risk factors), use of alternative therapy (i.e., biologics) prior to initiation of tofacitinib, prior and current medications, procedures (including screening and monitoring tests), ADD and duration of tofacitinib therapy will be examined to address the objectives.

Data source: The study population will be sourced from the French national health claims database, the Système National des Données de Santé (SNDS), which covers >99% (~65 million insures) of the French population from birth or immigration to death or emigration.

Study size: 480 to 1,062 patients per indication group (e.g., RA/PsA and UC) are needed to detect a minimum meaningful difference with 80% statistical power and a two-sided 5% significance level in the proportion of tofacitinib initiators with risk factors of interest across different reporting periods. In contrast, 240 to 426 patients per indication group are needed to detect a minimum meaningful difference with 80% statistical power and a two-sided 5% significance level in the composite risk factor scores. Based on preliminary assessment of data from the SNDS database, it is anticipated that approximately 8,000 RA or PsA and 2,000 UC patients who initiate tofacitinib will be captured through the end of the indexing period (e.g., December 2024).

Data analysis: The analysis will be conducted separately by indication of tofacitinib ("RA or PsA" and "UC," unless otherwise specified). Results will be provided as descriptive statistics such as count and proportion of patients having taken the recommended laboratory tests prior to initiating tofacitinib. Utilisation of tofacitinib in patients with VTE risk factors, patients 65 years and older, patients with CV risk factors and patients with malignancy risk factors will be stratified by reporting periods (VTE, CV and malignancy, and the JAKi reporting periods) in accordance with the distribution of the revised aRMM materials following the 2019 Article 20 referral, the 2021 signal procedure, and the 2022/2023 JAKi Article 20 referral to contextualise the changes in patterns of use. Comparative statistical analyses will be conducted to describe changes in the use of tofacitinib across reporting periods.

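### Section 9.5 takes the smallest n per scenario, so the stated requirements (160-354 and 80-142 per period) do not give 80% power for the smaller differences the protocol also classes as small

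*Protocol*

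**What the plan says.** Section 9.5 uses a class of 'small' effects to inform the minimum meaningful difference: OR from 1.5 to below 2 for proportions (Table 5 footnote), and Cohen's d from 0.2 to below 0.5 for the composite scores. It then fixes the requirement for proportions by the rule "Minimum sample size is determined based on the smallest sample size needed to detect a minimum meaningful difference per scenario of baseline proportion", and for scores by the parallel rule "Minimum sample size is determined based on the smallest sample size needed to detect a minimum meaningful difference per scenario of baseline variance".

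For proportions the result is 160 to 354 patients per reporting period. The Abstract repeats the totals: "480 to 1,062 patients per indication group (e.g., RA/PsA and UC) are needed to detect a minimum meaningful difference". For scores, "It is estimated that 80 to 142 patients per reporting period (240 to 426 total patients) per indication group" "are needed to detect a minimum meaningful difference with 80% statistical power" "and a two-sided 5% significance level".

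Section 9.5 closes by comparing these figures with about 8,000 RA/PsA and 2,000 UC initiators and concludes that the sample is sufficient. It also commits the MAH to notify the EMA if sufficient sample size is not reached.

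**The concern.** A minimum meaningful difference is the smallest change one would not want to miss, so the sample size that protects it is the largest n among the differences that qualify, not the smallest. Taking the smallest n moves the calculation to the most favourable tabulated difference and then labels it the minimum.

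Table 5 shows this directly. At baselines of 70%, 60% and 50% it labels both 10 and 15 points as small, and the rule picks 15. At 80%, 40% and 30% only 10 points is tabulated, so the supposed minimum changes between 10 and 15 points within one table.

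At stake is the sufficiency statement and the EMA notification. A reporting period, or a comparison of two periods, could be called adequate when it has less than an even chance of detecting a difference that the protocol itself calls small.

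**Working it through.** **Inputs (Section 9.5).** Two-sided alpha 0.05, power 80%, equal n per period, baselines of 30% to 80%, and the class limits given above. z values 1.96 and 0.8416, so (1.96 + 0.8416)² = 7.849.

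**Step 1: reproduce the plan.** For proportions, n = 7.849 × [p1(1−p1) + p2(1−p2)] / e², with p2 = baseline minus difference. For 70% to 55%: 7.849 × (0.21 + 0.2475) / 0.0225 = 159.6, giving 160. All nine rows of Table 5 reproduce. For scores, n = 2 × 7.849 × SD² / e². All 52 rows of Table 6 reproduce. The formulas are sound.

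**Step 2: which rows the rule selects.** The smallest n per baseline (80/70/60/50/40/30%) is 291/160/171/167/354/291, which is the stated 160-354. The smallest n per SD runs from 80 (SD 0.9, difference 0.40, d = 0.44) to 142 (SD 0.3, difference 0.10, d = 0.33), which is the stated 80-142.

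**Step 3: power for proportions at the selected n.** Power = Φ(e / √{[p1(1−p1) + p2(1−p2)] / n} − 1.96). For 70% to 60% with n = 160: 0.10 / √(0.45/160) = 1.886; Φ(1.886 − 1.96) = 47.0%.

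| Baseline | Selected n | Selected difference (OR) | Power, 10 points | n for 10 points (OR) | Power, OR 1.5 | n for OR 1.5 |
|---|---|---|---|---|---|---|
| 80% | 291 | 10 (1.71) | 80% | 291 (1.71) | 54.5% | 532 |
| 70% | 160 | 15 (1.91) | 47.0% | 354 (1.56) | 40.7% | 422 |
| 60% | 171 | 15 (1.83) | 46.3% | 385 (1.50) | 46.3% | 385 |
| 50% | 167 | 15 (1.86) | 45.5% | 385 (1.50) | 45.5% | 385 |
| 40% | 354 | 10 (1.56) | 80% | 354 (1.56) | 73.3% | 418 |
| 30% | 291 | 10 (1.71) | 80% | 291 (1.71) | 57.3% | 497 |

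**Step 4: power for scores at the selected n.** Power = Φ(d√(n/2) − 1.96). With d = 0.2, n = 80 gives Φ(1.265 − 1.96) = 24.4% and n = 142 gives Φ(1.685 − 1.96) = 39.2%. For 80% power, n = 2 × 7.849 / 0.04 = 392.4, giving 393 for any SD.

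**Step 5: labels in Table 6.** Eight of the 52 rows marked small have d below 0.2: SD 1.3 with 0.20 and 0.25; SD 1.2 with 0.20; SD 1.1 with 0.20; SD 1.0, 0.9 and 0.8 with 0.15; SD 0.6 with 0.10.

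**Step 6: does the threshold matter for any period?** Section 9.5 gives about 1,000 UC initiators to December 2020 and 2,000 to December 2024. *Assume* the other 1,000 accrue evenly over 48 months (20.83 a month). With the period lengths in Section 9.2.6, JAKi period 2 (5 months) has about 104, period 3 (16 months) about 333, and period 1 the remaining 2,000 − 104 − 333 = 1,563. The equal-n equivalent of two unequal groups is 2·n1·n2/(n1 + n2), exact for the score formula and approximate for proportions:
- period 3 against 1: 2 × 333 × 1,563 / 1,896 ≈ 549
- period 2 against 1: 2 × 104 × 1,563 / 1,667 ≈ 195
- period 2 against 3: 2 × 104 × 333 / 437 ≈ 158

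The first exceeds every restated figure. The second clears the selected n of 160-171 and all of 80-142, but not 291 or 393. The third clears 80-142 but not 393.

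**The case against.** The strongest reply is that these n do not set enrolment. Section 9.5 includes every eligible patient, and an equal three-way split of 2,000 UC patients is about 667 per period, above every restated figure. That stands. A reader might infer that the study itself has power of only 24-47%; the documents do not support that, and on the assumption in step 6 even the UC primary contrast for the JAKi periods is comfortable before any restriction to patients with risk factors.

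Three further limits also stand.
- A reader might extend power below 50% to the whole 160-354 range. It holds only at three of the six baselines. At 80%, 40% and 30% a 15-point fall has an OR of 2 or more and is no longer small, so 10 points was the only candidate on that grid and has its 80%.
- The selected rows are the largest *tabulated* differences, not the largest possible in the class: for SD 1.0 to 1.3 a further step of 0.05 would still be below d = 0.5.
- The protocol says the class informs the minimum. It never names OR 1.5 or d = 0.2 as the minimum, and the notification commitment gives no per-period threshold.

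None of this rescues the rule. Whichever minimum is meant, it cannot be 15 points where the same table also classes 10 points as small.

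**Conclusion.** The point holds as a faulty selection rule, not as an error in the formulas. The stated requirements do not give 80% power for the smaller differences that the protocol also classes as small:
- 45.5-47.0% for 10 points at baselines of 50-70% (n 160-171);
- 55-73% at OR 1.5 at baselines of 80%, 40% and 30%, where 10 points does have 80%;
- 24-39% at d = 0.2 across the whole 80-142 range.

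The stated maximum of 354 (1,062 in total) is also below the 385 (1,155) that Table 5 gives for 10 points at 60% and 50%.

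The powers use the protocol's own formulas with equal n, and describe a study of exactly the stated size. The practical consequence is confined to the sufficiency statement and the EMA notification. It bears most on the secondary comparisons involving short periods in UC, which rests on the even-accrual assumption in step 6. The JAKi outcome in Section 9.7.2.5.1 is further limited to UC patients with CV or malignancy risk factors, so its denominators are smaller than those shown. The mislabelled Table 6 rows change no stated requirement, since none is a selected row.

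**What to change.** In Section 9.5, name one minimum meaningful difference and apply it to every scenario:
- **Proportions:** if 10 points is declared the minimum, 291-385 per period (873-1,155 in total); if OR 1.5 is the minimum, 385-532 per period (1,155-1,596 in total). The two rules should not be mixed, because 291 corresponds to OR 1.71 and gives only 55-57% power at OR 1.5.
- **Scores:** at d = 0.2, 393 per period (1,179 in total) for any SD.

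Replace the rule of taking the smallest n, carry the new figures into the Abstract, and relabel the eight Table 6 rows with d below 0.2. Judge sufficiency for the EMA notification by comparing the restated n with the expected count in each reporting period and indication group, allowing for unequal period sizes, rather than with whole-study totals.

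The cost is text and less favourable stated figures. No additional patients or data are needed.

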9.7.2.4.1. Patients with venous thromboembolism risk factors

To describe changes in the utilisation of tofacitinib, this analysis will be stratified by the VTE reporting periods 1, 2 and 3.

The proportion of patients with one or more risk factors for VTE, identified prior to tofacitinib initiation, will be described and tabulated overall and by individual VTE risk factor (e.g., prior VTE and recent MI).

Logistic regression analyses will be used to calculate odds ratios along with their corresponding 95% confidence intervals and p values to formally compare the proportion of patients with VTE risk factors across VTE reporting periods 1, 2 and 3.

To enhance statistical power in detecting changes, a composite score for the VTE risk factors will also be generated by summing the individual VTE risk factors. Linear regression analyses will be employed to compare the VTE composite score across the VTE reporting periods. In addition to the summed composite score, the same analysis using a composite score weighting the risk factors may be considered in an exploratory fashion (weights will be developed and described in the SAP). Regression coefficients with their 95% confidence intervals and p values will be generated.

The proportion of patients diagnosed with UC, one or more VTE risk factors identified prior to tofacitinib initiation and no use of alternative therapy (i.e., biologic) prior to tofacitinib initiation whose ADD in Week 17 through Week 24, Week 25 through Week 32, Week 33 through Week 40 or Week 41 through Week 48 was >10 mg will be described and tabulated.

The proportion of patients who discontinue or continue to facitinib after developing one or more VTE risk factors while taking to facitinib will be described separately.

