9.7.2.4.3. Patients with cardiovascular risk factors

To describe changes in the utilisation of tofacitinib, this analysis will be stratified by the CV and malignancy reporting periods 1, 2 and 3. The proportion of patients with one or more CV risk factors, identified prior to tofacitinib initiation, will be described and tabulated overall and for each individual CV risk factor.

Logistic regression analyses will be used to calculate odds ratios along with their corresponding 95% confidence intervals and p values to formally compare the proportion of patients with CV risk factors across CV and malignancy reporting periods 1, 2 and 3.

To enhance statistical power in detecting changes, a composite score for the CV risk factors will also be generated by summing the individual CV risk factors. Linear regression analyses will be employed to compare the CV composite score across the CV and malignancy reporting periods. In addition to the summed composite score, the same analysis using a composite score weighting the risk factors may be performed in an exploratory fashion (weights will be developed and described in the SAP). Regression coefficients with their 95% confidence intervals and p values will be generated.

Proportions will be stratified by sex, age (≥65 years versus < 65 years) and prior use of alternative therapy (e.g., biologic), pending sufficient sample size.

The proportion of patients who discontinue or continue to facitinib after developing one or more CV risk factors while taking to facitinib will be described separately. The proportion will be further stratified by sex, age (≥65 years versus < 65 years) and prior use of alternative therapy (e.g., biologic), pending sufficient sample size.

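### The risk-factor score regressions make no allowance for unequal variances across reporting periods of very unequal size; with default standard errors the VTE intervals could be somewhat too narrow and the CV and malignancy intervals too wide

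*Protocol*

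**What the plan says.** Each composite score counts the yes/no risk factors that a patient carries at initiation (Protocol Table 3). Section 9.5 sizes the comparison with a two-sample t-test formula that has one common variance, "assuming equal sample sizes and variances between any two reporting periods". It reports that the SD at baseline mostly lay around 0.6 to 0.8. On the difference to detect, a Cohen's d "effect size of 0.2 to <0.5 (small effect) was used to inform the minimum meaningful difference". The result: "It is estimated that 80 to 142 patients per reporting period (240 to 426 total patients) per indication group".

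For the analysis, section 9.7.2.4.1 says: "Linear regression analyses will be employed to compare the VTE composite score across the VTE reporting periods". Section 9.7.2.4.3 says: "Linear regression analyses will be employed to compare the CV composite score across the CV and malignancy reporting periods". Section 9.7.2.4.4 does the same for the malignancy score. All three promise coefficients with 95% CIs and p values. None says how the standard errors are to be obtained, and section 9.7 leaves detailed methods to the SAP.

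Sections 9.2.4 and 9.2.5 set periods of 17, 17 and 50 months (VTE) and 42, 16 and 26 months (CV and malignancy).

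**The concern.** Ordinary linear regression on reporting period estimates one residual variance over all periods. That does little harm when the periods are of similar size. Here they are not, so a difference in variance between periods feeds directly into the standard error of the Period 3 versus Period 1 contrast.

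A difference is plausible. A factor with prevalence p contributes variance p(1-p), which shrinks as p falls below one half. Section 9.5 recognises this for proportions, where its formula adds p1(1-p1) and p2(1-p2), but gives the score, which is a sum of such factors, a single variance.

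The two sets of periods are then affected in opposite directions. For VTE, the long, low-variance Period 3 dominates the pooled figure while the short, high-variance Period 1 dominates the true error, so intervals come out too narrow. For CV and malignancy, Period 1 is the long period and intervals come out too wide. At stake is the coverage of intervals meant to show how far use in higher-risk patients has fallen.

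**Working it through.** **1. The plan's own figure.** n per period = 2(1.96 + 0.842)² SD²/difference². With SD 0.6 and difference 0.20: 2 × 7.849 × 0.36/0.04 = 141.3, so 142. With SD 0.9 and difference 0.40: 79.5, so 80. All 52 rows of Table 6 reproduce exactly.

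**2. Period sizes (assumed even accrual).** Section 9.5 gives about 4,000 RA/PsA initiators to December 2020 (36 months, 111.1 per month) and about 8,000 to December 2024 (a further 4,000 over 48 months, 83.3 per month).
- VTE Periods 1, 2, 3: 1,889, 1,889, 4,222.
- CV/malignancy Periods 1, 2, 3: 4,500, 1,333, 2,167.

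**3. Formulae.** Let v1, v2, v3 be the period variances.
- Pooled variance sp² = (n1v1 + n2v2 + n3v3)/(n1 + n2 + n3).
- Default SE = √[sp²(1/n1 + 1/n3)].
- True SE = √(v1/n1 + v3/n3).
- Coverage = 2Φ(1.96 × default SE/true SE) - 1.

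**4. Poisson-like case (assumption: the variance drops by as much as the mean, Period 2 halfway).** SD 0.6 and difference 0.20 give v = 0.36, 0.26, 0.16.
- VTE: sp² = 0.2308, default SE 0.01330, true SE 0.01512, ratio 0.88, coverage 91.5%.
- CV: sp² = 0.2892, default SE 0.01406, true SE 0.01240, ratio 1.13, coverage 97.4%.

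| Period 1 SD | Difference | VTE ratio (coverage) | CV ratio (coverage) |
|---|---|---|---|
| 0.6 | 0.10 | 0.947 (93.7%) | 1.053 (96.1%) |
| 0.6 | 0.15 | 0.916 (92.7%) | 1.089 (96.7%) |
| 0.6 | 0.20 | 0.880 (91.5%) | 1.134 (97.4%) |
| 0.7 | 0.15 | 0.941 (93.5%) | 1.060 (96.2%) |
| 0.7 | 0.20 | 0.918 (92.8%) | 1.087 (96.7%) |
| 0.8 | 0.15 | 0.957 (93.9%) | 1.044 (95.9%) |
| 0.8 | 0.20 | 0.940 (93.5%) | 1.062 (96.3%) |
| 0.8 | 0.30 | 0.903 (92.3%) | 1.105 (97.0%) |

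The largest Table 6 differences at SD 0.6 and 0.7 would go somewhat beyond these values, but they imply extreme falls. At SD 0.6 a difference of 0.25 takes the mean from 0.36 to 0.11, a 69% fall.

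**5. Without the Poisson assumption.** Take four independent factors at 45, 40, 10 and 5% in Period 1, 40, 35, 9 and 4.5% in Period 2, and 35, 30, 8 and 4% in Period 3 (assumed prevalences). The variances are 0.625, 0.592 and 0.550, the Period 1 SD is 0.79 and the mean falls by 0.23. The VTE ratio is 0.980 (coverage 94.5%) and the CV ratio 1.022 (95.5%). A fall half as large gives about 1% either way. The directions hold but the effect is small.

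**6. When it vanishes or reverses.** With equal variances, and so with no change between periods, the ratio is 1.00 and coverage 95%. If the main change is one factor falling from 60% to 50%, its variance rises from 0.24 to 0.25. With a total going from 0.335 to 0.345, the VTE ratio is 1.005 and the CV ratio 0.995.

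**7. The remedy.** In 3,000 simulated two-period data sets with Poisson means 0.64 and 0.29 and the VTE sizes above, ordinary intervals covered 91.5% and unequal-variance intervals 95.1%. With the CV sizes the figures were 97.3% and 94.9%.

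**8. Sample size.** With variances 0.36 and 0.16 and difference 0.20, n = 7.849 × (0.36 + 0.16)/0.04, about 102 per period against the tabulated 142. At 142 the power is about 91%.

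**The case against.** The strongest reply is that the protocol states nothing wrong. The equal-variance sentence is a planning assumption for Table 6. A reader might infer that it also fixes the analysis, but nothing in the text does so: robust standard errors are compatible with linear regression, and the choice could be made in the SAP. This stands, and it is why the point is conditional on default standard errors being used.

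A reader might also infer that the VTE intervals will be too narrow and the CV ones too wide as a matter of course. The documents do not support that. They give no score means, factor prevalences or period-specific SDs. The scores include common factors such as age 65 or over and hypertension, and section 9.5 expects 30 to 80% of initiators to carry at least one risk factor. A factor carried by more than half of patients can reverse the direction.

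Nor do the documents support two further readings. The type I error under no change is not inflated. Table 6 is not too small either: at equal n its common variance is conservative if the variance falls, so re-sizing gains nothing.

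Finally, the effect is modest. With SD 0.8, a difference of 0.35 and the VTE sizes, the true SE is about 0.020, so the estimate lies about 17 standard errors from zero, and no conclusion about whether use fell would change.

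The same formulae give larger errors for UC in the VTE comparison (ratios 0.77 to 0.91, coverage 86.8 to 92.6%). They arise because UC patients indexed before May 2019 are excluded (section 9.2.2), leaving about one month, or some 50 patients, in VTE Period 1. That is a separate design matter, which a robust variance does not cure.

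**Conclusion.** The point holds conditionally, as a minor improvement. If model-based standard errors are used and the score variance falls as risk factors become rarer, the RA/PsA Period 3 versus Period 1 intervals would be roughly 1-12% too narrow for VTE (coverage about 91.5-95%) and roughly 1-13% too wide for CV and malignancy. The upper ends rest on a Poisson-like score and a fall of more than half in its mean (0.36 to 0.16). The lower ends come from smaller falls in sums of yes/no factors. All figures assume even accrual of the section 9.5 projections. The concern is interval coverage when a real change occurs, not the validity of the test under no change and not the study size.

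**What to change.** Keep the same mean-difference regressions and add one sentence to section 9.7.2.4: standard errors, 95% CIs and p values for the composite-score comparisons use a heteroscedasticity-consistent variance (for example HC3). Leave Table 6 as it is. The estimates do not change, and the intervals remain valid whether the variance falls, rises or stays the same. The cost is that sentence and one option in the regression procedure, with no extra data or patients.
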